#### 8.8.3 Secondary and Exploratory Efficacy Analysis

Statistical tests to compare each APT-1011 dosing group with placebo will be performed for the secondary efficacy endpoints, but the corresponding p-values will be considered as descriptive rather than inferential. The secondary endpoints will be analyzed via a Cochran-Mantel-Haenzel test for categorical endpoints and analysis of covariance for change from baseline endpoints, except for the endpoint of time to relapse after initiation of double-blind treatment in Part 2, which will be analyzed using Kaplan-Meier methods.

As a secondary efficacy analysis, all 4 doses of active treatment will be pooled and compared to placebo with a one-sided test of two proportions.

Additionally,

a logistic regression model using both dose and frequency and dose-frequency interaction will be used to analyze the primary endpoint. Formal statistical hypothesis testing will be used to

Adare Pharmaceuticals SP-1011-002 APT-1011

evaluate treatment benefit with respect to the reduction in number of dysphagia episodes. For each dose that meets the criterion for statistical significance on the primary efficacy outcome, a Wilcoxon Rank-Sum test will be used to test whether the reduction in the number of dysphagia episodes from baseline is larger for the treatment group compared to the control. The hypothesis to be tested is:

 $H_0: R_{1i}(x) \leq R_{0i}(x)$ 

 $H_1: R_{1j}(x) > R_{0j}(x)$ 

Where  $R_{ij}(x)$  is the distribution function for the reduction in number of dysphagia episodes for treatment group i (=0 for control, 1 for treatment) and dose j. Holm's step-down procedure will be used to control the overall Type I error at 0.05, where the number of doses considered for inferential testing is equal to the number of doses that meet statistical significance for the primary efficacy analysis.

Statistical tests to compare each APT-1011 dosing group with placebo will be performed for other secondary efficacy endpoints, but the corresponding p-values will be considered as descriptive rather than inferential. The secondary endpoints will be analyzed via a stratified Cochran-Mantel-Haenzel test for categorical endpoints and analysis of covariance or Wilcoxon Rank-Sum tests for change from baseline endpoints, except for the endpoint of time to relapse after initiation of double-blind treatment in Part 2, which will be analyzed using Kaplan-Meier methods.

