16.1.2. MISSING DATA METHODS FOR PRIMARY EFFICACY VARIABLE

For the primary analysis of the primary efficacy variable, any subject who does not meet the definition of responder, will be classified as a non-responder. This includes subjects who withdraw from the study prior to the week 12 histological assessment.

The primary analysis of the primary efficacy variable is via a stratified Cochran-Mantel-Haenzel (CMH) test, as described in section 16.1.3.

A sensitivity analysis, described in section 16.1.4 will be performed with missing response data imputed using multiple imputation, assuming the data are missing at random.

Multiple imputation will be used to provide estimates of the common odds ratio, its 90% confidence interval and associated 1-sided p-value.

The dataset containing subject, dosing group, week 12 histologic response, the two randomization strata, history of asthma/allergy, baseline EREF score, and PPI status will be used as the basis for multiple imputations. Histologic response will be set to missing for those subjects who did not have a Week 12 result for peak eosinophils/HPF (and for whom response status was set to non-responder in the primary efficacy analysis).

The methodology which follows in this section are taken from a 2013 paper by Ratitch, Lipkovich and O'Kelly. The imputation method will be based on logistic regression using the MONOTONE statement of PROC MI in SAS

Author:

Version Number: 3.0

Version Date: 06NOV2019

Template No.: CS_TP_BS016 Revision 5 Reference: CS_WI_BS005

Page 30 of 70

as shown below.

The option NIMPUTE in the PROC MI statement will be used to specify the number of imputed datasets to be generated. The output dataset will contain 500 copies of the original dataset, with the observed values being the same across all datasets, and with imputed values varying from one dataset to another. These multiple copies will be identified by a new variable, Imputation, added to the output dataset by PROC MI.

The SAS Code to perform the imputations is provided below. The SEED and NIMPUTE value are explicitly stated here to enable results to be replicated and quality assured.

```
PROC MI DATA=datain OUT=datain mi SEED=1201913 NIMPUTE=500;
VAR dosegrp strata1 strata2 asthma EREF PPI response;
CLASS dosegrp strata1 strata2 response;
MONOTONE LOGISTIC;
RUN;
```

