16.2. SECONDARY EFFICACY

16.2.1. SECONDARY EFFICACY VARIABLES & DERIVATIONS

16.2.1.1. EoE sustained response: maintenance of ≤6 peak eosinophils/HPF at Weeks 26 and 52 for histologic responders at Week 12

For histologic responders at Week 12, maintenance of ≤ 6 peak eosinophils/HPF at each of Week 26 and Week 52 is defined as having ≤ 6 peak eosinophils/HPF (as per the primary efficacy variable in section 16.1.1), at each of Weeks 26 and 52 respectively.

Subjects who withdrew prior to each of Weeks 26 and 52 will be classified as non-responders at those visits.

Author:

Version Number: 3.0

Version Date: 06NOV2019

Template No.: CS_TP_BS016 Revision 5 Reference: CS_WI_BS005

Page 37 of 70

16.2.1.2. Change from baseline EREFs Total Score at Week 12, Week 26, and Week 52 For total esophagus:

- each of edema and stricture will be classified as either Grade 0 (absent) or Grade 1 (present)
- rings will be classified as Grade 0 (none), Grade 1 (mild), Grade 2 (moderate), Grade 3 (severe)
- each of exudates and furrows will be classified as Grade 0 (none), Grade 1 (mild), Grade 2 (severe)

Crepe paper esophagus and narrow caliber esophagus will each be classified as Grade 0 (absent) or Grade 1 (present).

Esophageal erosions will be classified as Normal, and each of Grade A through to Grade D based on the Los Angeles Classification, but not separately for the proximal and distal esophagus.

A total EREFs score will be derived as follows:

Component	Grade	Score
Edema*	Absent	0
	Present	1
Rings*	Grade 0 (none)	0
	Grade 1 (mild)	1
	Grade 2 (moderate)	2
	Grade 3 (severe)	3
Exudates*	Grade 0 (none)	0
	Grade 1 (mild)	1
	Grade 2 (severe)	2
Furrows*	Grade 0 (none)	0
	Grade 1 (mild)	1
	Grade 2 (severe)	2
Stricture*	Absent	0
	Present	1

Author:

Version Number: 3.0

Version Date: 06NOV2019

Template No.: CS_TP_BS016 Revision 5 Reference: CS_WI_BS005

Page 38 of 70

Crepe paper esophagus	None	0
	Present	1
Narrow caliber esophagus	None	0
	Present	1
Esophageal erosions (Los Angeles	Normal	0
Classification)	Grade A	1
	Grade B	2
	Grade C	3
	Grade D	4
Total score		Sum of the above (ranging from 0
		to 15)

- * For this component the grade/score will be based on the WORST result.

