- The change from baseline in the EREFs total score will be summarized as continuous variables, and analysis of covariance (ANCOVA) will be used to compare the mean change from baseline in each of the APT-1011 dosing groups to placebo, at the Week 12 visit, with the estimated mean difference, 90% confidence interval of the mean difference and 1-sided p-values provided. This statistical testing at Week 12 is considered descriptive only and no adjustments will be made for multiple comparisons.
- The ANCOVA models will include the factors described in section 7.1.

•

16.2.1.3. Peak eosinophils/HPF number <1 and <15 at Week 12, Week 26, and Week 52 Subjects who had withdrawn prior to each visit will not have results imputed, and percentages will be based on the number of subjects with EGD results assessed at the visit.

Subjects with a result of <1/HPF will also be counted as having a result of <15/HPF.

- 16.2.1.4. Change from baseline Global EoE Symptom Score at each post-baseline visit The global EoE symptom score, ranging from 0 to 10 will be provided directly to IQVIA Biostatistics with no derivation required. This will be retrieved from the diary.
- 16.2.1.5. Change from baseline in the number of dysphagia episodes at Week 12, Week 26 and Week 52

The number of dysphagia episodes for a subject will be determined from the 14 day evening diary completed prior

Author:

Version Number: 3.0

Version Date: 06NOV2019

Template No.: CS_TP_BS016 Revision 5 Reference: CS_WI_BS005

Page 39 of 70

to each of Week 12, Week 26 and Week 52. The number of episodes for each day will have 2 components a real time episode component along with the CRF entry of the number of dysphadia free days in the last 24 hours. First a day must be identified as a valid day. A day is considered valid if the subject awnsers yes to the CRF question "In the last 24 hours, did you have any difficulty with food or pills going down."

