16.2.1.11. Assessment of treatment failure and relapse, including

Percentage of histologic non-responders at Week 12, Week 26, and Week 52

Histologic non-responders are subjects who do not achieve \leq 6 peak eosinophils/HPF after assessment of at least 5-6 biopsies from the proximal and distal esophagus (\sim 3 each) where the HPF area is 235 square microns (40 magnification lens with a 22 mm ocular).

For each visit, subjects who have withdrawn from the study prior to the visit are classified as non-responders at that visit.

- Percentage of subjects requiring emergency endoscopic food dis-impaction by dose before Week 14, between Week 14 and Week 28, and between Week 28 and Week 52 – retrieved from EGD assessment before unscheduled visit
- Percentage of subjects requiring esophageal dilation by dosing group and part of the study retrieved from EGD assessment before unscheduled visit

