16.2.3. Analysis of Secondary Efficacy Variables

Statistical tests to compare each APT-1011 dosing group with placebo will be performed for some secondary efficacy endpoints as described in the following sections, but the corresponding p-values will be considered as descriptive rather than inferential. The analyses and summaries of secondary efficacy variables will be performed for FAS analysis set.

16.2.3.1. Analysis of EoE sustained response: maintenance of ≤6 peak eosinophils/HPF at Weeks 26 and 52 for histologic responders at Week 12

The frequency and percentage of histologic responders at Week 12 who maintained response at each of Week 26 and Week 52 will be provided for each randomized dosing group. Only histologic responders at Week 12 will be included in the summary.

No statistical testing will be performed.

16.2.3.2. Analysis of change from baseline PGIS and change from baseline in each of the EEsAI items trouble swallowing, duration of trouble swallowing and pain when swallowing

For each of the two PGIS questions (see section 16.2.1.9) and for the EEsAI items trouble swallowing frequency, duration of trouble swallowing and pain when swallowing, shift tables will be provided for the results at baseline and at each post-baseline visit, for each randomized dosing group. Data will not be not included for visits after a histologic non-responder at Week 12 had received single-blind (to subject) APT-1011 3 mg BID in Part 2.

No statistical testing will be performed.

16.2.3.3. Analysis of percentage of subjects with a peak eosinophils/HPF number <1 and <15 and percentage of subjects with 7-day EEsAI total score <20

The number and percentage of subjects in each of these categories will be presented by visit for each of the randomized dosing groups.

The summaries will only include data while subjects are receiving double-blind study drug. Data will not be included for visits after a histologic non-responder at Week 12 had received single-blind (to subject) APT-1011 3 mg BID in Part 2.

Patients who do not have assessments at the respective visits will not be included in the denominator for

Author:

Version Number: 3.0

Version Date: 06NOV2019

Template No.: CS TP BS016 Revision 5

Reference: CS WI BS005

Effective Date: 01Apr2018

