Copyright © 2009, 2010, 2012, 2016, 2018 IQVIA. All rights reserved. The contents of this document are confidential and proprietary to IQVIA Holdings Inc. and its subsidiaries. Unauthorized use, disclosure or reproduction is strictly proh bited.

Page 45 of 70

percentages.

No statistical testing will be performed.

16.2.3.4. Analysis of Change from baseline in each of Global EoE Symptom Score, Total EREFs Score, Number of Dysphagia Episodes, 7-day EEsAI total score, 7-day EEsAI VDQ and AMS subscores The change from baseline in each of Global EoE Symptom Score (see section 16.2.1.4), 7-day EEsAI total score (see section 16.2.1.6) and 7-day EEsAI VDQ and AMS subscores (see section 16.2.1.7) will be summarized as continuous variables, and analysis of covariance (ANCOVA) will be used to compare the mean change from baseline in each of the APT-1011 dosing groups to placebo, at the Week 12 visit, with the estimated mean difference, 90% confidence interval of the mean difference and 1-sided p-values provided. This statistical testing at Week 12 is considered descriptive only and no adjustments will be made for multiple comparisons. The ANCOVA models will include the factors described in section 7.1.

All these change from baseline analyses will only include data while subjects are receiving double-blind study drug. Data will not be not included for visits after a histologic non-responder at Week 12 had received single-blind (to subject) APT-1011 3 mg BID in Part 2.

For the analysis of change from baseline in the number of dysphagia episodes (see section 16.2.1.5) and dysphagia free days, for each dose that meets the criterion for statistical significance on the primary efficacy outcome, a Wilcoxon Rank-Sum test will be used to test whether the reduction in the number of dysphagia episodes from baseline is larger for the APT-1011 dosing group compared to the control.

Holm's step-down procedure (Holm, 1979) will be used to control the overall Type I error at 0.05, where the number of doses considered for inferential testing is equal to the number of doses that meet statistical significance for the primary efficacy analysis.

Holm's step down procedure will be implemented as follows:

Let the number of APT-1011 doses that meet statistical significance in the primary efficacy analysis be represented by d (where d is between 1 and 4 inclusive for this study).

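### The <1 and <15 eosinophils/HPF rates use only subjects with an EGD at the visit, while the ≤6 rate from the same biopsies counts missing as failure

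*SAP*

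**What the plan says.** **<1 and <15.** Protocol 6.2.8.2 names both as secondary endpoints at Weeks 12, 26 and 52. SAP 16.2.1.3 imputes nothing for withdrawn subjects: "percentages will be based on the number of subjects with EGD results assessed at the visit". SAP 16.2.3.3 repeats the rule: "Patients who do not have assessments at the respective visits will not be included in the denominator". It also leaves out visits after a Week 12 non-responder switches to single-blind 3 mg BID, and closes with "No statistical testing will be performed".

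**≤6.** SAP 16.1.2 makes every subject who is not a responder at Week 12 a non-responder: "This includes subjects who withdraw from the study prior to the week 12 histological assessment". For sustained response, SAP 16.2.1.1 says "Subjects who withdrew prior to each of Weeks 26 and 52 will be classified as non-responders at those visits". For the percentage of histologic non-responders, SAP 16.2.1.11 says "subjects who have withdrawn from the study prior to the visit are classified as non-responders at that visit". SAP 16.2.2 adds that Week 26 non-responders count as non-responders at Week 52.

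**Testing.** Protocol 8.8.3 says "The secondary endpoints will be analyzed via a stratified Cochran-Mantel-Haenzel test for categorical endpoints", with p-values treated as descriptive. SAP 3.3 lists changes from the protocol, but not the removal of this comparison.

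**The concern.** The three cut-points are nested: a subject with <1 also has ≤6, and a subject with ≤6 also has <15. Their rates in one arm should therefore rise in that order. Two missing-data rules break this.

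The subjects removed are not a random subset. Under Protocol 4.1.1, food impaction or withdrawal for worsening symptoms makes a subject a treatment failure who exits the study. An EGD at early termination does not bring that subject back, because SAP 6.3 does not re-map end-of-treatment visits and SAP 6.4 builds by-visit summaries from nominal visits.

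At stake is how the histologic depth of response reads across doses. Effect on histology, dose-response and Phase 3 dose selection are all secondary objectives (Protocol 3.2).

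**Working it through.** **Inputs**
- 20 subjects per arm (Protocol 8.1).
- ≤6 response of 60% on active and 10% on placebo, one-sided 0.05, power 97.5% (Protocol 8.1.1).
- 20% loss among responders by Week 26 (Protocol 8.1.1).
- Assumed, because neither document gives them: the number without a Week 12 EGD, and the number at <1 or <15.

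**1. The plan's own figure.** Two-proportion test with pooled variance: (0.50 − 1.645·√(2·0.35·0.65/20)) / √(0.6·0.4/20 + 0.1·0.9/20) = 0.2519/0.1285 = 1.96, so power = 0.975. The stated 97.5% reproduces and is untouched by this point.

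**2. Inflation.** Let n be the arm size, m the number without an EGD, x the number at ≤6 and k the number at <1. The plan reports x/n for ≤6 and k/(n−m) for <1. With missing as failure, <1 would be k/n, so the reported rate is larger by n/(n−m). With n = 20 and m = 1 to 4 this factor is 1.05, 1.11, 1.18 and 1.25. The same factor applies to <15.

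**3. Reversal of <1 against ≤6.** k/(n−m) > x/n is the same as k/x > (n−m)/n. The share of ≤6 responders who are also <1 must exceed the share with an EGD. For n = 20 and x = 12, so that ≤6 is always 60.0%:

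| Missing (assumed) | Smallest k that reverses | <1 as planned | <1, missing = failure |
|---|---|---|---|
| 1 | 12 | 12/19 = 63.2% | 60% |
| 2 | 11 | 11/18 = 61.1% | 55% |
| 3 | 11 | 11/17 = 64.7% | 55% |
| 4 | 10 | 10/16 = 62.5% | 50% |

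Under one rule <1 cannot exceed ≤6.

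**4. <15.** This is the looser cut-point and is expected to be higher under any rule. Only its size is affected: with 13 at <15 and 4 missing, 13/16 = 81% against 13/20 = 65%.

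**5. Active against placebo.** Take 10 active and 1 placebo subject at <1. With missing as failure the difference is 10/20 − 1/20 = 45.0 points. As planned:
- 2 missing in each arm: 10/18 − 1/18 = 50.0
- 5 active and 1 placebo missing: 10/15 − 1/19 = 61.4
- 1 active and 5 placebo missing: 10/19 − 1/15 = 46.0

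**6. Part 2.** On the protocol's assumptions, a 60% arm has 12 Week 12 responders and 12 × 0.8 = 9.6 with a Week 26 EGD on double-blind drug. The 1.5 mg HS arm (20%) has 4 × 0.8 = 3.2 and placebo 2 × 0.8 = 1.6. If none of the 20% lost has a Week 26 EGD, the factor is 1/0.8 = 1.25. At Week 52 the effect comes from the design: Week 26 non-responders have left, count as failures at ≤6, and are absent from the <1 and <15 denominators. Those who remain were responders at both earlier assessments.

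**The case against.** **The rule is explicit and the base would be visible.** The denominator is prespecified and stated twice, and the protocol sets no missing-data rule for these endpoints. SAP Appendix 1 requires a row or footnote whenever a percentage does not use the population count, so a reader could recompute count/N. Protocol 8.8.2 itself describes sustained response among completers. This stands in part: the observed-case choice does not contradict the protocol. But a footnote discloses the base without correcting the percentage, and the SAP chose missing = failure for ≤6, including for secondary endpoints. Repeating the analysis on ITT (SAP 16.4.1) does not help, because the denominator rule travels with the endpoint.

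**No inference is affected.** This stands. The primary analysis already counts missing as failure. A reader might infer that a controlled test was lost, but the protocol made these p-values descriptive, and SAP 16.2.3 says only some secondary endpoints are tested.

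**Size and direction are not established.** This also stands. A reader might infer that the stricter threshold will show the higher rate; it only can, and only for <1 against ≤6. Nor is there a fixed shift per missing EGD: 13/17 to 13/16 moves 4.8 points, 1/20 to 1/19 moves 0.3. It is also tempting to say that the bias is worst where subjects leave for lack of efficacy. Such arms tend to have low rates, where a smaller denominator changes few points; in step 5 the large distortion needs losses on active.

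**The protocol version differs.** SAP section 1 cites Amendment 2.1 of 06 September 2017, while the supplied protocol text carries 16 Jul 2019. The earlier text cannot be checked. In the supplied 8.8.3, one paragraph plans a plain CMH test and another a stratified one; both plan a comparison.

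**Conclusion.** The inconsistency is real and follows from the text alone: one biopsy count, three cut-points, two missing-data rules. As planned, the <1 and <15 rates exceed their missing-as-failure values by n/(n−m). The <1 rate overtakes the ≤6 rate whenever k/x exceeds the share with an EGD.

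The numerical examples rest on assumed missing counts and assumed <1 and <15 counts. The documents give no Part 1 dropout rate and no <1 rate, so the actual size is unknown. The effect on the active-placebo contrast depends on which arm loses subjects.

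The dropped CMH comparison is an unrecorded departure from the supplied protocol, without consequence for type I error. SAP version 3.0 is dated 06 November 2019, and Protocol 2.5 already reports the Week 12 outcome. A reader might infer that the choice followed sight of the data. The documents do not show that, since earlier SAP versions are not available.

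Overall this is a cheap improvement, not a threat to the primary result.

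**What to change.** 1. **Week 12.** On the FAS, count subjects without a Week 12 result as failures for <1 and <15, exactly as for ≤6.
2. **Weeks 26 and 52.** Use the denominator of the ≤6 sustained-response summary: Week 12 responders on double-blind drug, with withdrawn subjects counted as failures. State that denominator in the table title.
3. **Supplementary.** Keep the observed-case percentages, with their n, as a secondary display.
4. **Testing.** Either restore the protocol's descriptive stratified CMH comparison of each dose with placebo at Week 12, reported as the common odds ratio with 90% CI to match the primary analysis, or add a line to SAP 3.3 recording its removal.

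The cost is a change of wording in SAP 16.2.1.3 and 16.2.3.3, reuse of the primary analysis program, and one extra table. The reported <1 and <15 rates will be somewhat lower.

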#### 6.2.2 Daily Diary

A daily diary will be completed by the subject to assess the presence of dysphagia and questions related to its severity and associated pain. The diary will be completed by the subject for each episode and daily (in the evening) throughout the study. The daily diary will ask questions comprising the PROSE. The study will be used to define the measurement properties and definitions of symptom responder and non-responder for future studies as outlined in the exploratory endpoints (Section 3.3).

These data will be self-reported electronically by the subject, transferred automatically to the electronic patient-reported outcome (ePRO) vendor, and transmitted thereafter to Data Management.

English screenshots of the daily diary will be submitted in a separate file.

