# 8.5 Missing Data

Frequencies and comparisons of missing data by randomization and study visit will be summarized. Sensitivity analyses will be conducted for assessing the impact of missing data, including multiple imputation and tipping point analyses for the comparison of the dose with maximum utility versus placebo.

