7.3. MISSING DATA

Missing efficacy data for the primary efficacy analysis will be imputed as described in sections 16.1.2 and 16.1.4 of this SAP.

Missing components of certain efficacy variables will be imputed prior to analysis/summarizing. This is described in the relevant secondary and exploratory endpoint analysis sections.

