With a valid day from the evening diary the subject will add the real time episode component which comes from the swallowing difficulty. This component is the sum for each day of the CRF question "Did you just experience difficulty with food or pills going down?" The days will need to be readjusted if the time that they awnser the swallowing question and the time that they do the evening diary is more than 30 minutes difference. If the difference from episode time to diary time is greater than 30 minutes then this episode will be considered to have happened on the previous day.

Total dysphagia episodes will be the sum of the real time events for the previous 14 days of the subjects scheduled visit date.

A dysphagia free day will be classified if there are no real time events and no recalled episodes. Total dysphagia free days will be calculated as the sum of the previous 14 days of the subject scheduled visit date.

16.2.1.6. Change from baseline in 7-day EEsAI total score at Weeks 12, 26 and 52 The total score for the Eosinophilic Esophagitis Activity Index (EEsAI) will be derived as follows from the five separate components, described in section 16.2.1.7.

Item	Categorized Result Score		
Frequency of trouble swallowing	Never	0	
	1-3 times/week	15	
	4-6 times/week	27	
	Daily	31	
Duration of trouble swallowing	≤5 minutes	0	
	>5 minutes	6	
Pain when swallowing	No	0	
	Yes	15	
VDQ score	0	0	

Document:

Author:

Version Number: 3.0

Version Date: 06NOV2019

Template No.: CS_TP_BS016 Revision 5 Reference: CS_WI_BS005

Page 40 of 70

Item	Categorized Result	Score
	>0 - 2.5	12
	>2.5 – 5.0	19
	>5.0 – 7.5	21
	7.5 – 10.0	23
AMS score	0 – 5.0	0
	>5.0 – 7.5	9
	>7.5 – 10.0	25
Total score		100

16.2.1.7. Change from baseline in 7-day EEsAI subscores at Weeks 12, 26 and 52

There are five subscores of the EEsAI:

- o Frequency of trouble swallowing
- o Duration of trouble swallowing
- o Pain when swallowing
- Visual Dysphagia Question (VDQ) score
- o Avoidance, Modification and Slow Eating (AMS) score

Subjects were asked whether they had, in the past 7 days, eaten the following types of food:

- o Solid meat (steak, chicken, turkey, lamb)
- o Soft foods (pudding, jelly, apple sauce)
- o Dry rice (grains don't stick) or sticky Asian rice (without sauce)
- o Ground meat (hamburger, meat loaf)
- o Fresh white untoasted bread or similar foods (donut, muffin, cake)
- Grits, porridge (oatmeal), rice pudding
- o Raw, fibrous foods, not grated (apple, carrot, celery)

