16.2.2. MISSING DATA METHODS FOR SECONDARY EFFICACY VARIABLES

Subjects who did not complete Week 26 histological assessment will be classified as Week 26 non-responders. Subjects who were non-responders at Week 26 are to be withdrawn from the study at Week 26. These subjects and any subjects who either terminated the study early or did not completed Week 52 histological assessment will be counted as non-responders at Week 52.

Visitwise missing data will not be imputed in summaries or analyses of exploratory variables.

Rules for imputing missing data for the derivation of other individual parameters prior to summarizing or analyzing the variable, are provided in the relevant sections Error! Reference source not found. through to Error!

Reference source not found..

Author:

Version Number: 3.0

Version Date: 06NOV2019

Template No.: CS_TP_BS016 Revision 5 Reference: CS_WI_BS005

Page 44 of 70

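### SAP 16.2.1.5 scores dysphagia as a raw 14-day sum of real-time events, so a day with no entry counts as zero episodes; the main expected cost is distorted change and lost power.

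*SAP*

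**What the plan says.** The derivation in SAP 16.2.1.5 rests on four statements:

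- Valid day: "A day is considered valid if the subject awnsers yes to the CRF question" on swallowing difficulty in the last 24 hours.
- What a valid day contributes: "With a valid day from the evening diary the subject will add the real time episode component which comes from the swallowing difficulty".
- Total: "Total dysphagia episodes will be the sum of the real time events for the previous 14 days of the subjects scheduled visit date".
- Dysphagia-free day: "A dysphagia free day will be classified if there are no real time events and no recalled episodes".

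The diary has two entry streams. Protocol 6.2.2 says: "The diary will be completed by the subject for each episode and daily (in the evening) throughout the study".

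SAP 7.4 and 16.2.3.4 put the episode count under Holm's procedure with one-sided Wilcoxon tests. All other secondary testing is descriptive. Protocol 8.8.2 makes Part 2 mainly descriptive, so the inferential weight falls on Week 12.

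On missing data:

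- SAP 7.3 says "Missing components of certain efficacy variables will be imputed prior to analysis/summarizing" and refers to the endpoint sections. Section 16.2.1.5 contains no such rule.
- The pointer in SAP 16.2.2 is broken: the rules "are provided in the relevant sections Error! Reference source not found".
- The multiple imputation in SAP 16.1.2 is for the primary endpoint.
- Protocol 8.5 says "Frequencies and comparisons of missing data by randomization and study visit will be summarized". It also plans multiple imputation and tipping-point analyses for one dose against placebo.
- Inclusion Criterion 9 requires the diary on at least 5 of each 7 days in the last 14 baseline days. It applies to eligibility only.

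**The concern.** Followed literally, the text has three consequences.

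1. A day with no entry of either kind adds zero to the sum, exactly as a symptom-free day does.
2. The same blank day satisfies the dysphagia-free definition, which requires no evening answer.
3. The valid-day sentence and the total sentence disagree about a real-time event on a day without an evening 'yes'. One reading drops the event and the other counts it, so two programmers could produce different data from the same diary.

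Missed follow-up days therefore look like improvement, and missed baseline days hide it. Day-to-day gaps in completion add noise to the score. At stake is the derivation of the one secondary endpoint that the plan tests inferentially.

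**Working it through.** **1. The plan's own power figure.** Protocol 8.1.1 gives SDs of 4.5 and 7.5, 20 per arm and 80% power for a difference of 5.0, or 6.3 after Bonferroni over four doses.

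- Pooled SD = sqrt((4.5² + 7.5²)/2) = 6.18. Standard error = 6.18 x sqrt(2/20) = 1.96.
- One-sided noncentral t, 38 df: 80.7% at 5.0 (alpha 0.05) and 80.8% at 6.3 (alpha 0.0125). The stated figures reproduce.
- The planned Wilcoxon test with the same normal inputs gives about 77.7% and 77.4%.
- These inputs are per week, while the endpoint is a 14-day count.

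**2. What one lost day does.** Protocol 8.1.1 expects 25-35 episodes per week at baseline, so a lost baseline day removes 25/7 = 3.6 to 35/7 = 5.0 episodes. Take 30 per week and a 25% placebo reduction, the middle of the plan's 20-30%:

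- Full data: 60.0 - 45.0 = 15.0.
- Two follow-up days lost: 60.0 - (3.21 x 12) = 21.4.
- Two baseline days lost: (4.29 x 12) - 45.0 = 6.4. Inclusion 9 permits this, since up to 4 of the 14 days may be missing.

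**3. Equal misses in both arms.** Simulation, 20 v 20, one-sided Wilcoxon at 0.05.

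- From the plan: weekly rate 25-35; mean reductions of 25% (placebo) and 45% (active), the middles of its 20-30% and 30-60%.
- Assumed: Poisson daily counts, between-subject SD of the reduction 0.20, missed days at random, all events on them lost.

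| Week 12 days lost | Power, literal sum | Power, per observed day |
|---|---|---|
| 0% | about 74% | about 74% |
| 10% | about 67% | 69-73% across these rows |
| 20% | about 59% | |
| 30% | about 54% | |

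Results move a few points with the baseline loss assumed: with 10% of baseline days lost, the 20% row gives 62%. A second model used the plan's mean reductions (7.5 v 12.5 per week) and SDs on a 14-day scale, with no baseline loss. It shows a smaller effect: 77.6% with full data, 73.9% with 2 of 14 days lost in each arm and 68.8% with 4 of 14. Ideal proration there holds 77.4-78.2%.

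**4. Unequal misses, no true effect.** The first model, 25% reduction in both arms, 10% background misses and SD 0.08 or 0.20. Rejection at nominal 5%:

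- No extra misses: about 5%.
- One extra Week 12 day lost per active subject: 14-21%.
- The same with half the real-time events kept: about 9-11%.
- Missed evening diaries but all real-time events kept and counted: about 5%.
- One extra day lost per placebo subject: about 1%.

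The second model gives 28.6% and 0.25% for one day more on active and on placebo. The direction is stable but the size depends on the model.

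**5. Cost of a completion floor.** If a fraction m of days is missed at random, a window fails '5 of each 7' with probability 1 - [P(Bin(7, 1-m) >= 5)]². This is 5.1% at m = 10%, 27.4% at 20% and 58.1% at 30%, or about 1, 5-6 and 12 of 20 subjects per arm. With such subjects excluded (SD 0.08), power for the per-observed-day score against the literal sum is 91% v 87%, 81% v 79% and 56% v 69%.

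**The case against.** The case on the other side has several sound parts.

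- **A reader might infer that the rule favors the drug.** The documents do not support that. The test is biased only if lost days differ by arm and the real-time events on those days are lost too. The trial is blinded, no missed-day rate is given, and there is no stated reason to expect a difference. The bias could equally run against the drug.
- **A reader might infer that completed days cannot be counted.** The SAP's valid-day flag does merge a 'no' with a blank. But evening answers are captured electronically (Protocol 6.2.2) and the counts are drawn from the diary (SAP 6.9), so a completed 'no' can be identified in the data.
- **A reader might infer that no missing-data analysis is planned.** Protocol 8.5 plans summaries, multiple imputation and tipping-point analyses. They cover one dose against placebo and give no rule for diary days, so they do not change how a blank day is scored.
- **The Week 12 result may already be fixed.** SAP 4.2 makes the interim final for Week 12, so a later rule may not change the test.
- **A strict completion floor is not uniformly better.** Step 5 shows that it can cost more power than it recovers.

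These points limit the size and shape the remedy. None supplies a follow-up rule for days without entries or settles which events count.

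**Conclusion.** The point holds and should be fixed. The text gives a raw sum with no adjustment, a dysphagia-free definition that a blank day meets, and two sentences that conflict. The baseline eligibility floor and Protocol 8.5 repair none of these.

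The expected harm is distorted within-arm change and lost power. In the main illustration the loss is about 7 points at 10% lost days (74% to 67%) and 20 points at 30% (74% to 54%), of which per-observed-day scoring recovers most. In the second model it is about 9 points at 4 of 14 days (77.6% to 68.8%).

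These sizes rest on assumed missed-day rates, on the assumed spread, and on all events on missed days being lost. Bias of the test in either direction is possible but conditional on unequal misses with lost events. Confidence is high in the reading of the text and low in the size.

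**What to change.** **Derivation.**

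- Define a completed day as an evening diary answered yes or no.
- State that real-time events on a day without an evening diary are kept and that such a day counts as observed.
- Score episodes per observed day x 14. Set a window with no observed day to missing.
- Count a dysphagia-free day only on a completed 'no' with no real-time events, with completed days as the denominator.
- Report completed days by arm and window.
- Add a completed-days-only sensitivity analysis, because counting event-only days as observed over-represents days with events when episodes are rare.
- Repair the cross-reference in SAP 16.2.2.

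**Completion floor.** Treat any minimum as optional. Choose it after a blinded look at completion and use it as a sensitivity analysis.

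**Timing.** Protocol 2.5 already reports interim primary results, and SAP 4.2 makes the interim final for Week 12 and includes selected secondary endpoints. State whether the dysphagia endpoint was unblinded then and which reading was applied. If it was unblinded, keep that reading as the Week 12 test and present the per-observed-day score as a labelled sensitivity analysis. Apply the new rule prospectively to windows not yet analyzed, with a dated justification.

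**Cost.** SAP wording, programming and a few tables; no new data collection. Per-observed-day scoring assumes that missed days resemble observed ones, which should be stated.
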